2.5.2 Data handling conventions for secondary efficacy variables

Scheduled measurements ([Section 2.5.4](#)) of continuous variables collected during the study will be used in the analysis including those obtained after IMP discontinuation or introduction of rescue therapy. Continuous secondary efficacy endpoints will be analyzed with missing values imputed by the retrieved dropouts & washout imputation method or by the control-based copy reference imputation method according to the criterion described in [Section 2.4.4.1](#)

For the categorical secondary efficacy endpoints, data handling conventions are described in [Section 2.4.4.2](#).

2.5.3 Missing data

For categorical variables, patients with missing data are not included in calculations of percentages unless otherwise specified. When relevant, the number of patients with missing data is presented.

Derived variables will be considered missing if any of the original variables required to calculate them are missing. For example, if either a baseline assessment or an endpoint assessment is missing for a particular patient, then change from baseline at endpoint will be missing. Depending upon the assessment, analyses may not include all patients in the analysis population, because certain patients in the intended population may have missing data.

Incomplete date of first administration of double-blind IMP

Date/time of first administration is the first non-missing start date/time of double-blind IMP completed in the e-CRF “First dose IMP” module.

For patients who are randomized and dispensed a double-blind treatment kit but who are lost to follow-up just after Visit 3 (eg, only the treatment kit number is reported in the e-CRF “Exposure - treatment period” module without any dose information), the date of first administration will be imputed using the date of randomization. When a patient is randomized but not exposed, “Not taken” should be ticked in the e-CRF “First dose IMP” module.

Handling of computation of treatment duration if IMP end of treatment date is missing

For the calculation of the treatment duration, the date of the last dose of IMP is equal to the date of last administration reported on the end-of-treatment case report form page. If this date is missing, the exposure duration should be left as missing.

The last dose intake should be clearly identified in the case report form and should not be approximated by the last returned package date.

Handling of medication missing/partial dates

No imputation of medication start/end dates or times will be performed. If a medication date or time is missing or partially missing and it cannot be determined whether it was taken prior or concomitantly, it will be considered a prior, concomitant, and posttreatment medication.

Handling of adverse events/hypoglycemia with missing or partial date/time of onset

Missing or partial adverse event/hypoglycemia onset dates and times will be imputed so that if the partial onset date/time information does not indicate that the adverse event/hypoglycemia started prior to treatment or after the treatment-emergent adverse event period, the adverse event will be classified as treatment-emergent. No imputation of adverse event end dates/times will be performed. These data imputations are for categorization purpose only and will not be used in listings. No imputation is planned for date/time of adverse event resolution.

Handling of adverse events/hypoglycemia when date and time of first IMP administration is missing

When the date and time of the first double-blind IMP administration is missing, the day of randomization should be considered as the start date of TEAE period. The exposure duration should be kept as missing.

Handling of adverse events/hypoglycemia when IMP end of treatment date is missing

For the purpose of defining TEAE period, the date of the last administration of double-blind IMP is equal to the date of the last administration reported on the e-CRF “Treatment Status Library” page.

If the date of last administration reported on the eCRF “Treatment Status Library” page is

- Partially missing, it will be imputed with a date as late as possible before or on the date of last available information on e-CRF “Completion of End of Study/Follow-up”.
- Completely missing, it will be imputed with the date of last available information on e-CRF “Completion of End of Study/Follow-up” page.

If the date of last available information on eCRF “Completion of End of Study/Follow-up” page is

- Partially missing, it will be imputed with a date as late as possible.
- Completely missing, all adverse events occurred on or after the first administration of double-blind IMP will be considered as treatment emergent adverse events.

Handling of missing assessment of relationship of adverse events to IMP

If the assessment of the relationship to IMP is missing, then the relationship to IMP has to be assumed and the adverse event considered as such in the frequency tables of possibly related adverse events, but no imputation should be done at the data level.

Handling of missing severity/grades of adverse events

If the severity/grade is missing for 1 of the treatment-emergent occurrences of an adverse event, the maximal severity on the remaining occurrences will be considered. If the severity is missing for all the occurrences, a “missing” category will be added in the summary table.

Handling of potentially clinically significant abnormalities

If a patient has a missing baseline he will be grouped in the category “normal/missing at baseline.”

For PCSAs with 2 conditions, one based on a change from baseline value or a normal range and the other on a threshold value, with the first condition being missing, the PCSA will be based only on the second condition.

For a PCSA defined on a threshold and/or a normal range, this PCSA will be derived using this threshold if the normal range is missing; eg, for eosinophils the PCSA is >0.5 GIGA/L or $>ULN$ (if $ULN \geq 0.5$ GIGA/L). When ULN is missing, >0.5 GIGA/L should be used.

Measurements flagged as invalid by the laboratory will not be summarized or taken into account in the computation of PCSA values.

Linked adverse events that worsened or became serious

An AE that worsened or became serious will have a separate record in the data from the original event record with an AE identification number that links the new record to the original record. An

AE that worsened or became serious will be considered a new recurring AE in the summary of recurrent events or in the summary of events by time intervals.

Handling of missing data for continuous efficacy endpoints

Please See [Section 2.4.4.1](#) and [Section 2.4.4.2](#).

Handling of missing data for categorical secondary efficacy endpoints

Please See [Section 2.4.4.2](#).

2.5.4 Windows for time points/ Measurements for analysis

The following will decide how scheduled and/or unscheduled visits will be used in the analyses for efficacy variables and the by-visit summaries for safety variables (clinical laboratory data in [Section 2.1.4.4](#) and vital signs in [Section 2.1.4.5](#)).

Step 1 A scheduled measurement will be used if available; otherwise, an unscheduled measurement (including the end of treatment/study visit for those prematurely discontinued) will be used if it were on the same date as a scheduled visit.

Step 2 After step 1, if there are still no measurement for a given parameter at a scheduled visit, analysis window below ([Table 4](#)) will be applied to re-allocate a post-baseline unscheduled measurement to the scheduled measurement.

Table 4 - Analyses window definition

Scheduled visit post baseline	Targeted study day	Analysis window in study days
Week 2 (Visit 4)	14	2 to 20
Week 4 (Visit 5)	28	21 to 41
Week 8 (Visit 6)	56	42 to 69
Week 12 (Visit 7)	84	70 to 104
Week 18 (Visit 8)	126	105 to 153
Week 26 (Visit 9)	182	154 to 227
Week 39 (Visit 10)	273	228 to 318
Week 52 (Visit 11)	364	≥319

Study days are calculated from the day of first administration of double-blind IMP; the day of first administration of IMP (or the day of randomization if not exposed) is Day 1.

After applying the above time windows, if multiple assessments are associated to the same time point, the closest from the targeted study day will be used. In case of equality, the last measurement will be used. Re-allocated scheduled visits (ie, visit numbers) should be sequential if ordered by the date of measurement.

After Step 2, if there are still no measurement for a given parameter at a scheduled visit, data is considered missing for efficacy analyses, where multiple imputation would be applied as appropriately as described in [Section 2.4.4](#).

Reference day

The reference day for the calculation of extent of exposure, time to onset, and relative days will be the day of the first administration of double-blind IMP or the day of randomization if not exposed to double-blind IMP, denoted as Day 1.

Baseline definition for efficacy/safety data

For the safety analyses, the baseline for a given parameter is defined as the last available measurement (or the average of all measurements for creatinine and eGFR), including unscheduled assessments, assessed prior to the first administration of double-blind IMP. For BMD data, the baseline is defined as the measurement assessed prior to the date of first administration of double-blind IMP; if no such measurement, the one closest and within one month after the date of first administration of double-blind IMP will be used. For the efficacy analyses, the baseline for a given parameter is defined as the last available measurement (or the average of all measurements for creatinine and eGFR), including unscheduled assessments, assessed prior to the first administration of double-blind IMP or the last available value (or the average of all measurements for creatinine and eGFR) before randomization if not treated with double-blind IMP.

Summary statistics by visit for continuous efficacy endpoints

Summary statistics (number, mean, SD, SE, minimum, median, maximum) of continuous efficacy endpoints (observed data and change from baseline) will be provided at scheduled visits as per protocol. Summaries showing data by visit will be presented according to the visit number (or re-allocated visit number, see [Section 2.5.4](#)) and labeled with the targeted approximate day/week.

Last on-treatment value for laboratory variables and vital signs

The last on-treatment value is the final measurement assessed during the treatment epoch, regardless of the introduction of rescue therapy, including measurements at unscheduled visits. See [Section 2.1.4](#) and [Section 2.4.5](#) for details.

Display of safety data by visit (laboratory variables and vital signs)

Descriptive statistics (number, mean, SD, minimum, median, maximum) of quantitative laboratory variables and vital signs (observed data and change from baseline) during the TEAE period will be provided at scheduled visits. In addition, these summaries will also include a row for the “last value on-treatment” to describe the last available on-treatment value (see above). Summaries showing data by visit will be presented according to the visit number (or re-allocated visit number, see [Section 2.5.4](#)) and labeled with the targeted approximate day/week.

As specified in the study protocol, laboratory data from scheduled visits are reported by central laboratories. The local results will not be used in the efficacy analyses or in the definition of baseline for both safety and efficacy analyses. In the safety analyses, for parameters with PCSA defined based on normal range, local results will only be used in the PCSA summary if they are accompanied by a local laboratory normal range. For parameters with PCSA not defined based on normal range, local results will be used in PCSA summary as appropriately.

When a patient has more than 1 measurement from the central laboratory for the same laboratory parameter on the same date, the average of the measurements will be used. For the same laboratory parameter, if a patient has more than 1 measurement on different dates for the same scheduled visit, the value closest to the date of the visit will be used for the scheduled visit. When the values for the same scheduled visit are equidistant, the last value should be used for the scheduled visit. Similar rules will be applicable to a patient who has more than 1 set of measurements for the same vital sign parameter (ie, SBP, DBP, or HR) on the same date.

26-week double blind core treatment period

The 26-week double-blind core treatment period is the time from first administration of double-blind IMP to the last administration of double-blind IMP on or before Visit 9/Week 26 (or Day 182 if Visit 9/Week 26 date is missing). This is for defining EOT status at Week 26 and analyzing selected efficacy parameters (eg, rescued patients) during 26-week core treatment period.

TEAE period for the 26-week double blind core treatment period

The TEAE period for the 26-week double-blind core treatment period is 1) the time from the first administration of the double-blind IMP up to 10 days (1 day for hypoglycemia) after the last administration of IMP if the patient discontinued treatment on or before Visit 9 (or Day 182 if Visit 9 date is missing), or 2) the time from the first administration of the double-blind IMP to the administration at Visit 9/Week 26 (or Day 182 if Visit 9/Week 26 date is missing) if the patient remained treated beyond Visit 9/Week 26. This is for the purpose of safety analyses during the 26-week core treatment period.

26-week core study period

The 26-week core study period is the time from first administration of double-blind IMP to Visit 9/Week 26 (or Day 182 if Visit 9/Week 26 date is missing) or the end of TEAE period for the 26-week double-blind core treatment period (as defined above) whichever is later. This is for defining EOS status at Week 26.

Time to event analysis

For time to event analysis/KM plot, time to event (eg, treatment discontinuation, rescue therapy, hypoglycemia, ESRD, etc) is defined as the number of days from the date of the first administration of double-blind IMP (or the date of randomization if not exposed) to the start date of the first occurrence of the event during the respective analysis period.

Statistical Analysis Plan

Version: Final 3.0

Lexicon Pharmaceuticals Protocol No. EFC14837

Date of Issue: 21 November 2019

Covance Study ID:000000155205

Patients who did not experience any event during the respective analysis period are considered censored observations. The censoring rules are defined below.

Table 5 - Censoring date of time to event for 1st and 2nd step analysis

Time to event	Censoring date at Week 26 (1 st step analysis)	Censoring date at EOT/EOS (2 nd step analysis)
Treatment discontinuation due to any reason	Not applicable	EOT
Treatment discontinuation due to AE	Not applicable	EOT
Time to rescue	min (EOT, Date of W26 visit)	EOT
Time to severe or documented hypoglycemia	See Section 3	Min (EOT+1, EOS)
Time to ESRD	min (EOS, Date of W26/re-allocated W26 eGFR value)	EOS
Time to eGFR decrease	min (EOS, Date of W26/re-allocated W26 eGFR value)	EOS
Time to UACR progression/improvement	min (EOS, Date of W26/re-allocated W26 UACR value)	EOS

Note:

Day 182 will be used if Date of Week 26 visit (or date of W26/re-allocated W26) is not available.

Date of EOS will be used if date of EOT is not available; Last contact date will be used if date of EOS is not available.

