#### **10.1.2.4 On-site visit at Week 26 (Visit 9)**

The following procedures will be performed at this visit:

- Concomitant medications are assessed.
- Measurement of body weight.
- Complete physical examination. Vital signs. After 5 minutes resting, seated SBP, DBP, and HR will be assessed 3 times with at least 1 minute between each measurement (see [Appendix C](#) for details).
- IMP accountability and compliance for double-blind IMP.
- IRT to be notified IMP for re-supply.
- AEs/SAEs/AESI/EOSI and hypoglycemia (if any) are reported.
- Patients evaluated for glycemic rescue (see [Section 8.2.1](#)).
- Evaluate for 50% increase in creatinine.
- Diet and exercise instruction.
- Patient diary is collected and reviewed and a new one is dispensed. Instructions/training are provided as needed.
- Instructions on DKA symptoms and basic GU hygiene and hydration (see [Appendix B](#)) is provided.
- Fasting SMBG is assessed.
- 12-lead ECG.

- The following laboratory testing (by the central laboratory):
  - FPG
  - HbA1c
  - Urine pregnancy testing for WOCBP
  - Clinical chemistry (including amylase, lipase, fasting lipids, and uric acid) and hematology
  - Cystatin C
  - Fructosamine
  - NT-proBNP
  - Urinalysis (dipstick and microscopy)
  - Urine albumin, calcium, phosphorus, glucose, and creatinine
  - Collection of home urine for analysis of albumin, creatinine, calcium, phosphorus, magnesium, glucose, and albumin creatinine ratio.
- Additional laboratory testing at this visit:
  - Markers of intestinal transit and absorption (vitamins B6, B12, K, E, and A, serum folate, and ferritin)
  - Markers of bone and calcium metabolism: serum calcium (adjusted for creatinine), serum 25 hydroxyvitamin D, serum 1,25-dihydroxyvitamin D, serum phosphorus (adjusted for phosphorus), serum magnesium, iPTH, markers of bone resorption (serum NTX, serum  $\beta$ -CTX-1) and bone formation (serum P1NP and osteocalcin), and serum ALP
  - [REDACTED]
- Pre-dose PK (plasma concentration sample for sotagliflozin and sotagliflozin-3-O-glucuronide); an additional blood sample will be collected 3 hours after IMP administration for the assessment of creatinine (for eGFR) and for assessing plasma concentration of sotagliflozin and sotagliflozin-3-O-glucuronide.
- IMP is dispensed
- Patients are instructed to return to the site in the fasting state for Visit 10 (Week 39).

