#### **10.3.3 List of criteria for permanent treatment discontinuation**

Patients may withdraw from treatment with the IMP if they decide to do so, at any time and irrespective of the reason, or this may be the Investigator's decision. Patients should discuss stopping study medication with the site before doing so in order that questions can be addressed, glycemic therapy adjusted, and a follow-up assessment arranged. All efforts should be made to document the reasons for treatment discontinuation; this reason should be documented in the e-CRF.

The following reasons can lead to permanent discontinuation:

- At the patient's own request (ie, withdrawal of consent for treatment).
- If, in the Investigator's opinion, continuation with the administration of the study treatment would be detrimental to the patient's well-being.
- Intercurrent condition that requires permanent discontinuation of the study treatment as long as the abnormality persists and if the casual relationship of the concerned event and the IMP is possible (according to the Investigator's best medical judgment).
- Deterioration of renal function (defined as increase in serum creatinine > 50% from Baseline) that is not recovered after a temporary IMP discontinuation for 2 weeks.
- Patient requires renal replacement therapy (transplant or dialysis).
- Pregnancy (in female patients).
- Specific request of the Sponsor.

Any abnormal laboratory value will be rechecked immediately to confirm the result before a decision is made to permanent discontinue IMP for the concerned patient.

For patients who prematurely discontinue the IMP, the assessments planned at EOT visit ([Section 10.1.3.2](#)) will be performed at the Premature EOT Visit scheduled preferably prior to treatment discontinuation or as soon as possible after the time of discontinuation (at the latest at the next scheduled on-site visit). In the case of premature IMP discontinuation, no sample for measuring plasma concentration should be taken at the Premature EOT Visit, or at any subsequent

visit. The reason(s) for IMP discontinuation will be clearly specified. This Premature EOT assessment may occur at a regularly scheduled or at an unscheduled visit.

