- f Self-monitored blood glucose (SMBG) is to be performed fasting, at least 3 times per week from start of Run-in until end of Treatment Period including on day of each on-site study visit except Visit 4. Patients will also be requested to self-assess blood glucose levels whenever they experience symptoms of hypoglycemia. The SMBG will be presented as equivalent self-monitoring plasma glucose (SMPG).
- g The 12-lead ECG recordings should be obtained prior to IMP administration. The ECG will be evaluated as "normal" or "abnormal".
- h All laboratory assessments occur prior to dose of double-blind IMP. All visit dates will be scheduled based on the date of randomization with a ± 3 days visit window allowed during the Treatment Period. Chemistry panel: Hematology panel in Section 9.2.1.3.
- i Clinical chemistry laboratory tests are outlined in Table 2. Other chemistry tests will include amylase and lipase.
- j An additional blood sample will be drawn at Week 26 (Visit 9) and Week 52 (Visit 11), 3 hours after administering the dose of IMP for creatinine (for eGFR) and for assessing plasma concentration of sotagliflozin and sotagliflozin-3-O-glucuronide.
- k Serum pregnancy testing only at Screening; urine pregnancy testing subsequently. Serum pregnancy test results must be reviewed prior to beginning the Run-in phase for all women of childbearing potential (WOCBP). Any positive urine test results must be confirmed based on serum pregnancy test. The Investigator may perform additional tests at their discretion or as required by local regulations. For women of nonreproductive potential (Appendix A), follicle stimulating hormone (FSH) and/or estradiol levels should be tested if the definition of postmenopausal or premenopausal cannot be satisfied, eg, no medical document of hysterectomy or cessation of menses <12 months without an alternative medical cause.
- l Plasma concentration samples for sotagliflozin and sotagliflozin-3-O-glucuronide collected on Weeks 4, 18, 26, and 52 may be drawn with the other laboratory assessments but MUST be collected before administration of IMP. The time of the last intake of study drug prior to visits where PK samples are taken should be recorded by the patient in the patient diary. Patients should be reminded of this at visits preceding PK time points to ensure these details are captured. In the case of premature IMP discontinuation, PK samples should not be drawn at the Premature EOT Visit, neither at all subsequent visits.

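### SAP 2.5.4 averages same-date creatinine values, so by-visit creatinine and eGFR at Weeks 26 and 52 would mix a pre-dose and a 3-hour post-dose sample (minor)

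*SAP*

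**What the plan says.** **Two creatinine samples on one day.** Protocol 10.1.2.4 (Week 26) adds a blood sample "3 hours after IMP administration for the assessment of creatinine (for eGFR") and for drug concentration. Protocol 10.1.3.2 does the same at Week 52, and footnote j of the flow chart in SAP Appendix E repeats it: "3 hours after administering the dose of IMP for creatinine (for eGFR"). The routine chemistry that day is taken before dosing. Footnote h of the same chart says "All laboratory assessments occur prior to dose of double-blind IMP", and Protocol 10.1 agrees.

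**How several values are reduced to one.** SAP 2.5.4, in the part on displaying laboratory data by visit, says that if a patient has more than one central-laboratory value "for the same laboratory parameter on the same date, the average of the measurements will be used". It does not mention time relative to dose. The same section opens with a two-step selection for efficacy variables and by-visit safety summaries. Step 1 takes a scheduled measurement if there is one. Step 2 moves unscheduled measurements into windows where none exists.

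**Baseline.** Creatinine and eGFR baselines average all values obtained before the first double-blind dose (SAP 2.1.1 and 2.5.4).

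**Where the values go.** SAP 2.4.5.4 summarises all laboratory variables and their changes by visit and names creatinine and eGFR as candidates for trend plots. SAP 2.4.4.3 summarises eGFR by visit, overall and by CKD stratum, and counts patients with more than 50% decline at each visit. SAP 2.4.6 separates pre-dose from 3-hour values for drug concentrations. There is no matching instruction for creatinine.

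**The concern.** A change from baseline should compare like with like. Baseline holds no value taken after a double-blind dose, and the other on-treatment visits have pre-dose chemistry only. If Weeks 26 and 52 use an average of a pre-dose and a 3-hour value, the eGFR change at the two milestone visits carries half of any short-term creatinine movement after dosing. Trend plots then join points of two kinds. Averaging also hides what the extra sample could show, since the SAP plans no separate summary of it. Renal function is a main interest in a trial of patients with CKD stage 3, so the visit value should be settled by a written rule and not at programming.

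**Working it through.** The plan states no figure to reproduce. The check follows one patient through the rules and then sizes the effect.

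**1. Tracing the patient.** The patient has a pre-dose and a 3-hour creatinine at Week 26, both dated the same day. SAP 2.5.4 treats laboratory data from scheduled visits as central-laboratory data.
- *Safety summaries (SAP 2.4.5.4).* The averaging rule applies under its own heading. The Week 26 value is (pre-dose + 3-hour)/2.
- *Efficacy eGFR (SAP 2.4.4.3).* Step 1 asks for a scheduled measurement. Both samples are planned at the visit, so Step 1 does not clearly choose between them. Averaging is then the likely result, but it is inferred.

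**2. Inputs for size.** The MDRD formula in SAP 2.5.1 makes eGFR proportional to creatinine^-1.154. The 3-hour change in creatinine, r, is not in the documents; 0, ±2% and ±5% are assumptions.

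**3. Formulas.** Averaged creatinine = pre-dose × (1 + r/2). Hence averaged eGFR = pre-dose eGFR × f, with f = (1 + r/2)^-1.154. The analysed value reaches a 50% decline when pre-dose eGFR × f = 0.5 × baseline, that is, at a pre-dose decline of 1 - 0.5/f.

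**4. Numbers.** For r = +5%: f = 1.025^-1.154 = 0.9719. Then 45 × 0.9719 = 43.7, a shift of -1.3. The threshold is 1 - 0.5/0.9719 = 48.6%. For r = -5%: f = 0.975^-1.154 = 1.0296. Then 45 × 1.0296 = 46.3, a shift of +1.3. The threshold is 1 - 0.5/1.0296 = 51.4%.

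| Assumed r | Shift at eGFR 35 | Shift at 45 | Shift at 55 | Pre-dose decline counted as 50% |
|---|---|---|---|---|
| -5% | +1.0 | +1.3 | +1.6 | 51.4% |
| -2% | +0.4 | +0.5 | +0.6 | 50.6% |
| 0 | 0 | 0 | 0 | 50.0% |
| +2% | -0.4 | -0.5 | -0.6 | 49.4% |
| +5% | -1.0 | -1.3 | -1.5 | 48.6% |

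Shifts are in mL/min/1.73 m2. Averaging the two eGFR values instead of the two creatinine values gives almost the same result: -1.2 or +1.4 at 45 for r = +5% or -5%. If only the pre-dose sample is used, the shift due to sampling time is zero.

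**The case against.** **Step 1 may already pick the pre-dose sample.** Footnote h places laboratory assessments before dosing and footnote j calls the 3-hour draw additional. One can therefore read the scheduled measurement as the routine chemistry. This reading is possible, so a reader who infers that no SAP rule can give the pre-dose value goes too far. It is not secure either, because the 3-hour sample is itself planned at the visit and collected for eGFR.

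**The averaging rule belongs to safety displays.** This is true of its heading. The paragraph just before it does mention efficacy ("The local results will not be used in the efficacy analyses"), but only to exclude local results, which does not carry same-date averaging into efficacy. The point is therefore firm for the safety summaries and only probable for SAP 2.4.4.3.

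**The 26-week safety period would exclude the sample.** For patients who continue treatment, the core treatment-emergent period runs only "to the administration at Visit 9/Week 26". However, SAP 2.4.5 presents by-visit central-laboratory summaries for the entire 52-week treatment period only, so this boundary does not remove the Week 26 post-dose value from them.

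**A stronger reading.** A reader might infer from "In case of equality, the last measurement will be used" that the post-dose value alone would be analysed. The text does not support this. That sentence breaks ties after the Step 2 windows, and those re-allocate unscheduled values when a visit has no measurement. A patient with a Week 26 pre-dose creatinine does not get that far.

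**Materiality.** The endpoints are descriptive, and a time-of-day shift common to all arms largely cancels against placebo. This stands and sets the grade. An acute drug effect on creatinine would not cancel.

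**Conclusion.** The point holds as a minor one. For by-visit safety summaries of creatinine and eGFR, a stated rule mixes pre-dose and post-dose samples at Weeks 26 and 52. For the efficacy eGFR change and the counts of more than 50% decline, the SAP leaves the choice open and averaging is the likelier outcome.

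On an assumed 3-hour creatinine change of up to 5% either way, the shift is 1.0 to 1.6 mL/min/1.73 m2 at most across eGFR 35 to 55, and the effective 50% threshold moves by about 1.4 percentage points. With no 3-hour change the shift is zero. The documents support the mismatch in sampling time but not its size or direction.

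The primary and tested secondary endpoints are untouched. The eGFR-based part of ESRD and the sustained eGFR events require at least 30 days' persistence or adjudication, so one averaged visit value would not decide them.

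**What to change.** Add two sentences to SAP 2.5.4, along these lines: *Averaging of same-date values does not apply across nominal sampling times. At Weeks 26 and 52 the pre-dose sample is the visit value for by-visit creatinine and eGFR, change from baseline, and more than 50% decline in eGFR.* Optionally, summarise the 3-hour creatinine and eGFR separately by treatment group, as SAP 2.4.6 does for drug concentrations.

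No new data are needed, because the pre-dose sample is already collected. SAP 1.6 records that the first-step analysis has been run and reported for top-line results. Any Week 26 creatinine or eGFR table from that step that used averaged values would need a rerun, with the change noted in the SAP history.
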